3. STUDY ENDPOINTS AND ANALYSES

Statistical Analysis Plan (SAP) for Clinical Study AP-017

3.1 Primary Endpoint:

The primary endpoint assesses the effect of Ampion compared to placebo on prevention of need for mechanical ventilation or death prior to day 28. This is measured as the occurrence of mechanical ventilation or death by Day 28.

Let π_A and π_S represent the rate of this outcome for Ampion and control during the first 28 days after randomization. Then it is desired to demonstrate that the mechanical ventilation and death rate for Ampion is different than the corresponding rate for the control. Formally, this is presented as:

$$H_0: \pi_A = \pi_S \text{ versus } H_A: \pi_A \neq \pi_S$$

This will be tested utilizing the appropriate chi-square test or Fisher's exact test utilizing PROC FREQ with the EXACT option, if necessary.

Also, the median time to mechanical ventilation or death will be tested for difference between the two groups via the log-rank test. The test will be performed using PROC LIFETEST. The time to event distributions in each group will be estimated using the method of Kaplan and Meier.

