4.4 Inclusion Criteria

Patients should fulfill all the following inclusion criteria:

1. Male or female, ≥ 18 years old.
2. Diagnosed with COVID-19, as evaluated by laboratory diagnostic test or diagnosis based on radiological clinical findings.
3. Baseline severity categorization of severe or critical COVID-19 infection per FDA Guidance for developing drugs and biological products for COVID-19 (February 2021):
 - a) Severe COVID-19:
 - Symptoms suggestive of severe systemic illness with COVID-19, which could include shortness of breath or respiratory distress
 - Clinical signs indicative of severe systemic illness with COVID-19, such as respiratory rate ≥ 30 per minute, heart rate ≥ 125 per minute, $\text{SpO}_2 \leq 93\%$ on room air at sea level ($\text{SpO}_2 \leq 90\%$ at altitude) or $\text{PaO}_2/\text{FiO}_2 \leq 300$
 - b) Critical COVID-19:
 - Oxygen delivered by high-flow nasal cannula (heated, humidified, oxygen delivered via reinforced cannula at flow rates > 20 L/min with fraction of oxygen ≥ 0.5) or
 - Non-invasive mechanical or endotracheal mechanical ventilation
4. Informed consent obtained from the patient or the patient's legal representative.

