9.3 Data presentation

9.3.1.1 Demographic and Baseline Characteristics:

Demographic (e.g., age, sex, race, ethnicity) and baseline characteristics (e.g., weight, height, comorbidities) summarized using descriptive statistics, overall and by treatment group for the ITT and safety analysis population.

9.3.1.2 Medical History and Physical Examination:

The number and percent of participants with past and current medical disorders at the time of randomization will be presented overall and by treatment group for the ITT and safety analysis population.

9.3.1.3 Concomitant Medications or Treatments:

The number and percent of subjects receiving concomitant medications or therapies prior to and during the study and at the final visit will be tabulated and presented overall and by treatment group for the ITT analysis population.

Concomitant medications/treatments will be summarized using descriptive statistics and will be presented by type of drug (WHO DRUG classification) overall and by treatment group for the safety and ITT analysis populations. There should be no significant differences in the use of concomitant treatments between groups. All concomitant therapies will be recorded to be able to compare any inadvertent imbalances between the groups.

9.3.1.4 Safety Data:

Safety data will be presented by treatment arm. Safety data will be evaluated by changes in vital sign measurements, laboratory assessments, and the frequency and severity of AEs. Concomitant medication will be recorded for safety. AEs will be collected from baseline to Day 60. The severity of AEs (mild, moderate, severe), relatedness (related, possibly related, unrelated) along with the duration, action taken, and outcome (e.g., study withdrawal) will also be recorded.

All data collected under this study protocol will be included in the assessment of patient safety. Missing or incomplete AE data will assume greatest relationship to study drug and/or severity.

Remaining safety data will be collected from enrollment through index hospitalization until hospital discharge (or in-hospital death). Safety data will be tabulated and presented overall and by treatment group for the safety analysis population.

9.3.1.5 Efficacy Data:

The efficacy of treatment on the clinical course and outcome of COVID-19 will be evaluated by treatment arm. Summaries will be performed by severity (severe or critical), individually, and combined.

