2.4 Sample Size

The trial is designed to enroll up to approximately 200 patients across two treatment arms (active or control), with 100 subjects per arm, randomized 1:1 using a random allocation sequence stratified by COVID-19 disease severity (severe or critical). An interim analysis of the data is planned after 30 subjects (approximately n=15 subjects per arm) to evaluate the relative effect. At the interim analysis, the sample size may be re-estimated to determine the additional number of patients required for adequate power to meet the chosen effect size for the primary endpoint.

The number of participants is selected based on the effects observed for the primary endpoint, prevention of need for mechanical ventilation or death prior to day 28. A study recently reported in Lancet Respiratory Medicine with 243 hospitalized patients receiving the placebo for COVID-19 found 22% did not achieve day 28 ventilation-free survival (Lancet Respir Med 2021; [https://doi.org/10.1016/S2213-2600\(21\)00494-X](https://doi.org/10.1016/S2213-2600(21)00494-X)). In the AP-014 study, a lower rate (8%) was observed for subjects receiving inhaled Ampion. Assuming the same proportions (8% for Ampion and 22% for control) by Day 28, with 100 subjects per group, a two-sided 5% significance level, and using a z-test with unpooled variances, then under binomial enumeration the power to detect this difference is about 81.3%.

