3.2 Secondary Endpoints

3.2.1 Change in ordinal scale from baseline through Day 7, Day 14 and Day 28.

The hypotheses to be tested are:

$$H_0: \mu_A = \mu_S \text{ versus } H_A: \mu_A \neq \mu_S$$

Where μ_A and μ_S represent the ordinal scale shift through day 7, 14, and 28 for Ampion and Placebo after randomization. The difference between Ampion and Placebo with respect to the change from baseline at day 7, 14, and 28 will be tested utilizing a Wilcoxon rank-sum test via PROC NPAR1WAY. To assess any potential time trends, an exploratory repeated measures analysis of variance will be performed with terms for treatment, time and the interaction between the two. This will be done utilizing PROC GLM with the REPEATED option.

3.2.2 Change in NEWS2 score from baseline through Day 7, or discharge if earlier.

The hypotheses to be tested are:

$$H_0: \mu_A = \mu_S \text{ versus } H_A: \mu_A \neq \mu_S$$

Where μ_A and μ_S represent the mean change from baseline in the NEWS2 score assessment through day 7 for Ampion and Placebo after randomization. The difference between Ampion and Placebo with respect to the change from baseline at day 7, or discharge if earlier, will be tested utilizing a Wilcoxon rank-sum test via PROC NPAR1WAY. To assess any potential time trends an exploratory repeated measures analysis of variance will be performed with terms for treatment, time and the interaction between the two. This will be done utilizing PROC GLM with the REPEATED option.

3.2.3 Percentage of participants who progress to respiratory failure by Day 28.

The hypotheses to be tested are:

$$H_0: \pi_A = \pi_S \text{ versus } H_A: \pi_A \neq \pi_S$$

Statistical Analysis Plan (SAP) for Clinical Study AP-017

Let π_A and π_S represent the percentage of patients who have respiratory failure for Ampion and control during the first 28 days after randomization.

This difference will be tested utilizing the appropriate chi-square test or Fisher's exact test utilizing PROC FREQ with the EXACT option, if needed.

Also, the median time to respiratory failure will be tested for difference between the two groups via the log-rank test. The log-rank test will be performed using PROC LIFETEST; and the estimation of the time-to-event distributions will be performed using the method of Kaplan and Meier.

3.2.4 Percentage of participants who require Intensive Care Unit (ICU) admission by Day 28; ICU-free days through Day 28; ICU length of stay (LOS) from ICU admission to discharge.

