There are two endpoints in this set. Hypotheses about both will be tested independently. The first hypothesis about the percentage of patients who are admitted to the ICU involves all patients. The second hypothesis involves only patients who are admitted to the ICU. Since it is not known how many many patients will be admitted to the ICU, the testing of the second hypothesis will be considered exploratory and not part of the hierachial testing scheme.

The first hypotheses to be tested is:

$$H_0: \pi_A = \pi_S \text{ versus } H_A: \pi_A \neq \pi_S$$

Where π_A and π_S represent the percentage of patients who are admitted to the ICU for Ampion and Placebo during the first 28 days after randomization. The difference between Ampion and Placebo will be tested via an appropriate chi-square test or Fisher's exact test utilizing PROC FREQ with the EXACT option, if needed.

The second hypothesis to be tested is:

$$H_0: \text{Median}_A = \text{Median}_S \text{ versus } H_A: \text{Median}_A \neq \text{Median}_S$$

Where Median_A and Median_S are the median ICU length of stay for the Ampion and placebo groups. Assuming there is no censoring, this will be tested using the Wilcoxon rank sum test via PROC NPAR1WAY. If censoring occurs, e.g., death, then the log rank test will be used based on PROC LIFETEST.

3.2.5 Modulation of cytokine levels from baseline to Day 5.

The hypotheses to be tested are:

$$H_0: \mu_A = \mu_S \text{ versus } H_A: \mu_A \neq \mu_S$$

Where μ_A and μ_S represent the mean percent change from baseline in the cytokine levels at day 5 for Ampion and Placebo after randomization. The difference between Ampion and Placebo with respect to the percent change from baseline at day 5 will be tested utilizing a two sample t-test via PROC TTEST. To assess any potential time trends an exploratory repeated measures analysis of variance will be performed with terms for treatment, time and the interaction of the two. This will be done utilizing PROC GLM with the REPEATED option.

Statistical Analysis Plan (SAP) for Clinical Study AP-017

3.2.6 Hospital length of stay.

The hypotheses to be tested are:

$$H_0: \text{Median}_A = \text{Median}_S \text{ versus } H_A: \text{Median}_A \neq \text{Median}_S$$

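### Randomisation is stratified by severity but no planned test uses the stratum: a minor efficiency gain at almost no cost, if severity is prognostic

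*SAP*

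**What the plan says.** SAP 2.4 describes patients as "randomized 1:1 using a random allocation sequence stratified by COVID-19 disease severity (severe or critical"; protocol 3.1, 3.4, 4.1 and 9.1 agree.

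The tests do not carry the stratum forward:

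- **Primary endpoint (SAP 3.1):** "This will be tested utilizing the appropriate chi-square test or" Fisher's exact test when needed. Protocol 9.4.1 reads the same way.
- **Time to event (SAP 3.1):** "Also, the median time to mechanical ventilation or death will be tested for difference between the two groups via the log-rank test", as a plain two-group comparison.
- **Respiratory failure (SAP 3.2.3):** "This difference will be tested utilizing the appropriate chi-square test or" Fisher's exact test, and then "Also, the median time to respiratory failure will be tested for difference between the two groups via the log-rank test".
- **ICU admission (SAP 3.2.4):** "The difference between Ampion and Placebo will be tested via an appropriate chi-square test or" Fisher's exact test.

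Severity enters the analysis only descriptively. Protocol 9.3.1.5 says "Summaries will be performed by severity (severe or critical), individually, and combined", and protocol 9.4.2 tabulates endpoints by severity cohort. SAP section 8 adds no stratified or adjusted analysis.

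**The concern.** A factor is normally used to stratify randomisation because it is expected to predict outcome. Here that is plausible from the definitions alone. The critical stratum is defined by respiratory support at entry, and protocol 4.4 includes "Non-invasive mechanical or endotracheal mechanical ventilation" in it, while the primary endpoint is mechanical ventilation or death by Day 28.

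If severity is prognostic and the arms are balanced within strata, the pooled chi-square test uses a variance that includes the between-stratum part, which the design has already removed. The test then spends less than its allotted alpha and gives up some power. At stake is efficiency, not validity.

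A smaller point sits alongside. The SAP gives no rule for moving from chi-square to Fisher, so the primary test is not fully fixed in advance.

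**Working it through.** **Inputs from the documents.** Rates of 22% and 8%, 100 per arm, two-sided 5%, stated power 81.3% (SAP 2.4). Final alpha is about 0.049 in SAP 6.1 and 0.047 in protocol 9.2.3.

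**Assumptions, not in the documents.** Critical share 20%, 30% or 50%; critical-to-severe odds ratio (OR) 1 to 10; common treatment odds ratio; stratum rates solved so that the overall rates stay at 22% and 8%; exact balance within strata.

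**Step 1: the plan's figure.** Enumerating two Binomial(100) arms with the unpooled z-test at alpha 0.05 gives 81.28%, which matches 81.3%. Pearson's chi-square also gives 81.28%. At the planned final alpha, Pearson has 81.2% (0.049) or 80.2% (0.047).

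**Step 2: why the pooled test is conservative.** Take 30% critical and OR 5. The control rates are 13.05% (severe) and 42.88% (critical): 0.7 × 0.1305 + 0.3 × 0.4288 = 0.22. Suppose both arms have these rates.

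- Pearson's variance factor: 0.22 × 0.78 = 0.1716.
- True factor under balance: 0.7 × 0.1305 × 0.8695 + 0.3 × 0.4288 × 0.5712 = 0.1529.
- Ratio 0.1529 / 0.1716 = 0.891, with square root 0.944.
- The nominal cut-off 1.969 therefore acts as 1.969 / 0.944 = 2.085, a two-sided size of about 3.7% instead of 4.9%. Exact enumeration gives 3.66% for Pearson and 4.91% for CMH.

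**Step 3: power by full enumeration of the two-stratum tables.** In stratum h, with m patients per arm, N = 2m, a Ampion events and t total events, the CMH statistic is |Σ(a − t/2)| / √Σ[t(N − t)m² / (N²(N − 1))].

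At 30% critical and alpha 0.049:

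| OR | Pearson | CMH | Gain (points) | Gain over 20–50% critical |
|---|---|---|---|---|
| 1 | 81.17% | 81.15% | 0.0 | 0.0 |
| 2 | 81.34% | 81.48% | 0.1 | 0.1 |
| 3 | 81.63% | 82.23% | 0.6 | 0.4 to 0.6 |
| 5 | 82.18% | 83.98% | 1.8 | 1.1 to 1.8 |
| 10 | 83.21% | 87.02% | 3.8 | 2.1 to 3.9 |

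At alpha 0.047 the gains over the same shares are −0.1 to −0.2, 0.3 to 0.4, 1.0 to 1.1, 1.7 to 2.3 and 2.9 to 4.6 points. In patients, to match CMH at 100 per arm the pooled test needs 102 per arm at OR 3, 103 to 105 at OR 5 and 106 to 113 at OR 10.

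**Step 4: log-rank.** Simulation used 60,000 trials per scenario, exponential times, censoring at Day 28, no drop-out and alpha 0.049. Stratified minus pooled power is 0.0 to −0.1 point at OR 1, 0.3 to 0.4 at OR 2, 0.8 to 0.9 at OR 3, 1.7 to 2.1 at OR 5 and 2.7 to 4.3 at OR 10.

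**Step 5: chi-square or Fisher.** At the final analysis (alpha 0.049) Pearson has 81.2% power and Fisher 74.9%. A rule that switches when any expected cell count is below 5 would fire with probability 0.00014%. At the interim (15 per arm, alpha 0.001) Pearson rejects in 0.23% of trials and Fisher in 0.05%.

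**The case against.** The strongest reply is that nothing is broken. The pooled test is valid, and at an odds ratio of 2 or 3 the gain is worth at most two patients per arm. That stands, and it is why the point is called minor.

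The gain also depends on two unknowns, and the critical stratum may be small. Protocol 4.5 excludes a clinical diagnosis of respiratory failure (with a resource-limitation qualifier), and protocol 2.4.1 speaks of treating patients before they become critical. At 5% critical the gain falls to 0.04, 0.17, 0.59 and 1.79 points at odds ratios 2, 3, 5 and 10; at 10% critical it is 0.06, 0.28, 1.03 and 2.98. This shrinks the benefit but does not reverse it.

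Third, stratifying is not strictly free. At alpha 0.047 and an odds ratio of 1, CMH loses 0.1 to 0.2 point, or 0.27 at 5% critical. The protocol synopsis allows the allocation ratio to be adjusted during enrolment, so exact balance within strata is not assured. If the split is left wholly to chance, Pearson is no longer conservative (size 4.8% to 5.1%). CMH then loses 0.6 point at an odds ratio of 1 and 0.1 to 0.3 at 2, but gains 0.5 to 0.7 at 3, 1.7 to 2.4 at 5 and 3.3 to 5.5 at 10. That is an extreme case for a trial that stratifies its randomisation.

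Finally, the SAP's wording about an appropriate chi-square test could be read to cover CMH. If that is the intention, writing it down costs nothing.

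**Conclusion.** The concern holds as a minor improvement. The omission is plain in both documents. The benefit is about half a point of power at moderate prognostic strength and roughly 1 to 4 points if severity is strongly prognostic, assuming 20% to 50% critical and balance within strata; it is smaller if few critical patients enrol. Under stratified randomisation the loss if severity does not matter is at most about 0.3 point.

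The trial question does not change: with arms balanced within strata, the Mantel-Haenszel risk difference equals the crude difference. The existing power statement is not undermined.

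Confidence is high on the omission and the calculations. The size of the gain remains conditional on the assumed stratum share and odds ratio. The missing Fisher rule matters only if Fisher were used at the final analysis despite adequate counts. How patients already ventilated at entry count towards the endpoint is a separate question, not settled here.

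**What to change.** 1. In SAP 3.1, name one primary test: CMH stratified by severity as randomised, reported with the Mantel-Haenszel risk difference and a 95% confidence interval. An interval at the final-test alpha would keep interval and test in step, once the 0.047 and 0.049 figures are reconciled.
2. State the fallback: a stratified exact test only if any expected count in the pooled 2×2 table is below 5.
3. Stratify the log-rank tests in SAP 3.1 and 3.2.3 in the same way and, for consistency, the binary tests in SAP 3.2.3 and 3.2.4. The hospital-stay test in 3.2.6 can take the stratum too. ICU stay is exploratory and limited to admitted patients, so it can be left as it is. Whether to stratify the Wilcoxon tests in 3.2.1 and 3.2.2 is a further choice that was not evaluated here.
4. List the change in SAP 9.

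**Cost.** A SAP edit and one variable already collected for randomisation; no extra patients or data. For the primary test the SAP edit may suffice, because protocol 9.1 leaves analysis details to the SAP. For binary secondary endpoints protocol 9.4.2 names Fisher's exact test, and the SAP already departs from that without listing it in section 9. Aligning the protocol text would need a written amendment approved by the sponsor, the ethics committee and the health authorities (protocol 10.3). Make the edit before the 30-subject interim, which uses unblinded data (SAP 6.2).

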5.1.2 Baseline (Day 0)

The following procedures will be performed at Baseline (first assessment prior to treatment):

- Confirm eligibility (review inclusion/exclusion criteria).
- Randomize patient to study arm.
- Demographics (age, sex, race, height and weight)
- Concomitant medications/therapies
- Vital signs: heart rate, systolic and diastolic BP, body temperature, respiratory rate
- SpO₂ and supplementation oxygen mode/flow rate
- ECG monitoring (telemetry) or 12-lead ECG: record aberrant changes in waves/ intervals
- Hematology, biochemistry tests
- Cytokine and chemokine assays
- Ordinal scale and NEWS2 assessments
- AEs

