4. DEFINITIONS

4.1 Adverse Event:

An adverse event (AE) is defined as any undesired medical occurrence in a patient or clinical investigation patient receiving a pharmaceutical product and which does not necessarily have a causal relationship with this treatment. An AE can therefore be any unfavorable sign and unintended sign (including an abnormal laboratory finding), symptom, or disease temporarily associated with the use of a study drug, whether or not related to the study drug.

AEs will be graded for severity using the following categories. Missing grade will be assigned a grade of 3 (severe) in tabulations.

- **Grade 1 (MILD):** The symptom is barely noticeable to the study patient and does not influence performance or functioning. Concomitant medication is not ordinarily indicated for relief of mild AEs.
- **Grade 2 (MODERATE):** The symptom is of sufficient severity to make the study patient uncomfortable and to influence performance of daily activities. Concomitant medication may be indicated for relief of moderate AEs.
- **Grade 3 (SEVERE):** The symptom causes severe discomfort, sometimes of such severity that the study patient cannot continue in the study. Daily activities are significantly impaired or prevented by the symptom. Concomitant medication may be indicated for relief of severe AEs.

Relationship to study drug will be coded using the following categories. Missing relatedness will be assigned to related in tabulations.

- **Unrelated:** The adverse event is unlikely to have been caused by study drug.
- **Possibly related:** It is unclear whether the adverse event may have been caused by study drug.
- **Related:** The adverse event is likely to have been caused by study drug.

4.2 Serious Adverse Event:

A serious adverse event (SAE) is defined as an adverse event that

- Results in death
- Is life-threatening (patient is at immediate risk of death from the event as it occurred)

Statistical Analysis Plan (SAP) for Clinical Study AP-017

- Requires prolongation of existing hospitalization
- Results in persistent or significant disability/incapacity
- Results in a congenital anomaly/birth defect

4.3 Treatment-Emergent AE:

A treatment-emergent AE (TEAE) is any AE that begins or increases in severity after the initial dose of study drug.

4.4 Age:

Subject's age is defined as its integer value in years at enrollment.

4.5 Baseline:

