8.3 Demographic and Baseline Characteristics

Age, gender, race, height and weight, and comorbidities will be summarized by treatment arm for all subjects receiving study drug, using descriptive statistics.

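### The primary test is valid and meets its stated power, but pre-specified adjustment for age, already recorded at Day 0, would add robustness and perhaps 0 to 5 points of power

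*SAP*

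**What the plan says.** The primary endpoint is mechanical ventilation or death by Day 28, with a two-sided hypothesis on the two event rates. SAP 3.1 specifies: "This will be tested utilizing the appropriate chi-square test or Fisher's exact test utilizing PROC FREQ with the EXACT option, if necessary". Protocol 9.4.1 specifies the same test. The SAP adds a log-rank comparison and names no covariate or stratum for it.

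Age is in the Day 0 procedures of protocol 5.1.2: "Demographics (age, sex, race, height and weight". SAP 4.4 defines it: "Subject's age is defined as its integer value in years at enrollment". Its only planned use is descriptive (SAP 8.3): "Age, gender, race, height and weight, and comorbidities will be summarized by treatment arm for all subjects receiving study drug, using descriptive statistics".

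Randomisation is stratified by severity alone (SAP 2.4): "with 100 subjects per arm, randomized 1:1 using a random allocation sequence stratified by COVID-19 disease severity (severe or critical". Severity is also absent from the primary test.

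The sample size in SAP 2.4 rests on these assumptions: "Assuming the same proportions (8% for Ampion and 22% for control) by Day 28", at "a two-sided 5% significance level, and using a z-test with unpooled variances". It concludes that "under binomial enumeration the power to detect this difference is about 81.3" percent. SAP 8.6.1 classes any analysis of variables not described in the plan as post hoc.

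**The concern.** Eligibility is any adult of 18 or older (protocol 4.4), and nothing in the randomisation balances age. If age predicts ventilation or death, two things follow.

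- An adjusted test has more power on average than the crude one.
- In any single trial, a chance age difference between arms moves the crude result in one direction or the other.

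The second matters more for how the result is read. If the arms turn out to differ in age and no adjustment was written in beforehand, an age-adjusted analysis would be post hoc under SAP 8.6.1 and would carry little weight.

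**Working it through.** **Inputs from the documents.** 100 per arm, event rates 8% and 22%, two-sided 5% (SAP 2.4). Expected events: 8 + 22 = 30.

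**Assumptions, because the documents give no figures.** Standardised, normally distributed age; a logistic-linear age effect equal in both arms; an odds ratio (OR) of 1 to 3 per SD of age; no dropout; severity not modelled.

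**1. The plan's own figure.** Summing Binomial(100, 0.08) × Binomial(100, 0.22) probabilities over all tables that the unpooled z-test rejects gives 81.28%, against 81.3% stated. It reproduces. Pearson chi-square also gives 81.28%; Fisher's exact test gives 75.8%.

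**2. Average power with age in the model.** Intercepts were solved so that the marginal rates stay at 22% and 8%, with 20,000 simulated trials per row (Monte Carlo standard error about 0.3 points). The standardised risk difference is the mean over all patients of the predicted risk on Ampion minus the predicted risk on control, with an influence-function variance.

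| OR per SD | Chi-square | Likelihood ratio | Standardised risk difference | Wald |
|---|---|---|---|---|
| 1.0 | 81.39% | 81.51% | 81.34% | 79.85% |
| 1.3 | 81.76% | 82.20% | 81.98% | 80.64% |
| 1.5 | 80.85% | 81.90% | 81.72% | 80.21% |
| 2.0 | 81.01% | 83.20% | 83.06% | 81.80% |
| 2.5 | 81.48% | 84.88% | 84.86% | 83.63% |
| 3.0 | 81.28% | 86.14% | 86.03% | 84.90% |

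The likelihood-ratio gain over chi-square is +0.1, +0.4, +1.1, +2.2, +3.4 and +4.9 points. Other simulation runs gave up to +2.6 at OR 2.0. A Wald test loses 1.5 points when age has no effect and gains only 3.6 at OR 3.

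The variance of the risk difference falls by about 5% at OR 2.0 and 12% at OR 3.0. A 5% reduction is worth 100/(1 − 0.05) = 105 patients per arm instead of 100.

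**3. Size.** With 15% in both arms (10,000 runs), the likelihood-ratio and standardised tests rejected in 4.9% to 5.5% of trials, against 4.7% to 5.2% for chi-square.

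**4. Chance imbalance.** The standard error of the difference in mean age is √(1/100 + 1/100) = 0.14 SD. Ampion is older by more than that in about one trial in six. Power in those trials:

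| OR per SD | Chi-square | Age-adjusted likelihood ratio |
|---|---|---|
| 1.5 | 75.4% | 82.3% |
| 2.0 | 71.5% | 83.7% |
| 2.7 | 67.6% | 84.7% |

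When Ampion is younger by the same margin, chi-square power rises to 87% to 92%, while adjusted power stays at about 82% to 85%. A repeat simulation agreed within about 1 point.

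The size of the shift can be checked by hand. One SD of imbalance moves the crude risk difference by roughly ln(OR) × average p(1 − p). At OR 2 that is 0.693 × (0.22 × 0.78 + 0.08 × 0.92)/2 = 0.085, or about 0.08 once individual risks are averaged over age. An imbalance of 0.14 SD therefore moves it by about 0.14 × 8 = 1.1 points, against a 14-point target.

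**5. The interim.** With about 15 per arm (SAP 6.1), the chance of no Ampion events at an 8% rate is 0.92^15 = 29%. The treatment log odds ratio then has no finite estimate.

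**The case against.** The strongest reply is that nothing is wrong. The chi-square test is valid under randomisation, addresses exactly the marginal hypotheses stated, and reaches its planned power. No part of the plan relies on adjustment. All of that stands.

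A reader might infer that the plan throws away power that could be had for nothing. The documents do not support this. Neither calls age prognostic, gives an age-outcome association or gives an age distribution. At OR 1.5 or below the average gain is about 1 point or less. Nor is adjustment quite free: null rejection may rise by a few tenths of a point, and a likelihood-ratio test of a conditional effect can occasionally disagree with an interval for the marginal risk difference. The Wald loss is avoided by specifying likelihood ratio.

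It is also fair to say that age is not the first covariate to add. Severity is the randomisation stratum and is missing from the primary test. Leaving chi-square or Fisher open moves power by 81.3 − 75.8 = 5.5 points, more than age gains anywhere in the OR 1 to 3 range. Both deserve attention. Neither removes an age imbalance, so they are reasons to put severity in the same model and not reasons to leave age out.

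**Conclusion.** The point holds as an optional but inexpensive improvement. The crude test is sound; a pre-specified age-adjusted analysis would make the result less dependent on chance age imbalance, and would raise average power by about 0 to 5 points over an assumed OR of 1 to 3 per SD. If age is weakly prognostic, the gain is close to zero.

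The size rests entirely on that assumed range and on the modelling assumptions listed with the inputs. The simulations used alpha 0.05; the final alpha is about 0.049 in SAP 6.1 and 0.047 in protocol 9.2.3, where chi-square power is 81.2% and 80.2%. The effect of adding severity was not computed.

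**What to change.** Before unblinding, and preferably before the interim, which SAP 6.2 says uses unblinded data, amend SAP 3.1 as follows:

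- **Final primary analysis:** logistic regression of the Day 28 event on treatment, severity stratum and continuous age, tested by likelihood ratio. With 30 expected events and three terms, this is 10 events per term.
- **Estimate:** the standardised (marginal) risk difference with 95% CI and a named variance estimator, such as the influence-function variance used in the check. State that the likelihood-ratio test decides if the two disagree.
- **2x2 test:** keep it as a sensitivity analysis and as the test at the 30-patient interim, where the model would be unreliable. Say there whether it is chi-square or Fisher.

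Record the change in SAP section 9 and align protocol 9.4.1. The cost is SAP wording, a short program and, under protocol 10.3, a written protocol amendment with its approvals. No new data are needed.
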